3.2 Study schema

Primary Objective:

- a) Effects of Durvalumab on systemic immune response to HPV and tumor associated antigens
- b) Effects of Durvalumab on immune regulatory mechanisms.
- c) Association between immune-regulatory miR in plasma and saliva and immune response.

3.3 Study Oversight for Safety Evaluation

Although no interim analysis is planned, each study patient will be very carefully monitored for safety and treatment toxicity. Strict Durvalumab treatment discontinuation rules will apply. The study team will ensure that patients do not develop consistently toxicities of \geq grade III that exposes them to unnecessary and unjustified risks, including but not limited to the risk to delay or compromise the curative surgical intervention.

Should more than 3 patients develop toxicity \geq grade III (except infusion reaction) or have delays in surgical treatment due to toxicities related to treatment with Durvalumab, the study will be discontinued.

4. SUBJECT SELECTION

4.1 Inclusion criteria

For inclusion in the study subjects must fulfill all of the following criteria:

- Histologically or cytologically confirmed HNSCC of the oral cavity (OC; more than 90% patients have HPV negative cancer) or oropharynx (about 60-80% of patient have HPV positive cancer).
- Presence of radiologically or clinically documented disease. All radiology studies must be performed within 28 days prior to registration.
- Any stage, considered candidates for surgery and planned for surgery either by robotic or by standard surgical technique.
- Documentation of HPV tested by PCR (resulted or pending).
- Willing to provide consent for an additional tissue biopsy for research purposes, to allow a part of their surgical tumor tissue to be utilized for research (in case tumor tissue has not already been saved in the Tumor Tissue Bank), and to donate samples of blood and saliva collected weekly through the treatment.
- All patients must have provided informed consent for correlative studies.
- ECOG performance status of 0, 1 or 2.
- Patients must have no prior exposure to immune-mediated therapy, including anti-CTLA-4, anti-PD-1, anti-PD-L1, or anti-programmed cell death ligand 2 antibodies, excluding therapeutic anticancer vaccines.
- At least 1 lesion, not previously irradiated, that can be accurately measured at baseline as ≥10 mm in the longest diameter (except lymph nodes, which must have a short axis ≥15 mm) with CT or MRI or clinical measurement and that is suitable for accurate repeated measurements as per RECIST 1.1 guidelines.
- Previous surgery is permitted provided that a minimum of 28 days (4 weeks) have elapsed between any major surgery and date of registration, and that wound healing has occurred.

Clinical Study Protocol Drug Substance Durvalumab (MEDI4736) Study Number **ESR-15-11576** Edition Number 5 Date 05/23/16 WFU Date 03/31/17

- Organ and marrow function as defined below:
 - Absolute neutrophil count (ANC) $\geq 1.5 \times 10^{9}/L$;
 - Platelet count $\geq 100 \times 10^9$ /L;
 - Hemoglobin \geq 9.0 g/dL;
 - Serum bilirubin ≤ 1.5 x ULN (institutional upper limit of normal)
 - Total Bilirubin is less than or equal to ULN, except the case in which the elevated total bilirubin is not a sign of liver disease, such as the Gilbert Syndrome, in which case a Total Bilirubin less than or equal to 2X ULN is acceptable.
 - AST and ALT \leq 2.5 x ULN;
 - Serum creatinine CL>40 mL/min by the Cockcroft-Gault formula (Cockcroft and Gault 1976) or by 24-hour urine collection for determination of creatinine clearance:

Males:

Creatinine CL = $\frac{\text{Weight (kg) x (140 - Age)}}{\text{(mL/min)}}$. 72 x serum creatinine (mg/dL)

Females:

Creatinine CL = $\frac{\text{Weight (kg) x (140 - Age)}}{72 \text{ x serum creatinine (mg/dL)}}$ x 0.85

- Female subjects must either be of non-reproductive potential (ie, post-menopausal by history: ≥60 years old and no menses for ≥1 year without an alternative medical cause; OR history of hysterectomy, OR history of bilateral tubal ligation, OR history of bilateral oophorectomy) or must have a negative serum pregnancy test upon study entry.
- In accordance with NCIC CTG policy, protocol treatment is to begin within 2 working days of patient registration
- Written informed consent and any locally-required authorization (e.g., HIPAA in the USA, EU Data Privacy Directive in the EU) obtained from the subject prior to performing any protocol-related procedures, including screening evaluations.
- Age \geq 18 years at time of study entry.

• Subject is willing and able to comply with the protocol for the duration of the study including undergoing treatment and scheduled visits and examinations including follow up.

4.2 Exclusion criteria

Subjects should not enter the study if any of the following exclusion criteria are fulfilled:

- Involvement in the planning and/or conduct of the study (applies to both AstraZeneca staff and/or staff at the study site). Previous enrolment in the present study
- Participation in another clinical study with an investigational product during the last 6 mo.
- Any previous treatment with a PD1 or PD-L1 inhibitor, including durvalumab
- Receipt of any anti-cancer therapy (chemotherapy, immunotherapy, endocrine therapy, targeted therapy, biologic therapy, tumor embolization, monoclonal antibodies, other investigational agent) within the last 6 mo. (before the first dose of Durvalumab).
- Mean QT interval corrected for heart rate (QTc) ≥470 ms calculated from 3 electrocardiograms (ECGs) using Frediricia's Correction
- Current or prior use of immunosuppressive medication within 28 days before the first dose of durvalumab, with the exceptions of intranasal and inhaled corticosteroids or systemic corticosteroids at physiological doses, which are not to exceed 10 mg/day of prednisone, or an equivalent corticosteroid
- Any unresolved toxicity (>CTCAE grade 2) from previous anti-cancer therapy. Subjects with irreversible toxicity that is not reasonably expected to be exacerbated by the investigational product may be included (e.g., hearing loss, peripherally neuropathy)
- Any prior Grade ≥3 immune-related adverse event (irAE) while receiving any previous immunotherapy agent, or any unresolved irAE >Grade 1
- Active or prior documented autoimmune disease within the past 2 years NOTE: Subjects with vitiligo, Grave's disease, or psoriasis not requiring systemic treatment (within the past 2 years) are not excluded.
- Active or prior documented inflammatory bowel disease (e.g., Crohn's disease, ulcerative colitis)
- History of primary immunodeficiency
- History of allogeneic organ transplant
- History of hypersensitivity to Durvalumab or any excipient

Clinical Study Protocol Drug Substance Durvalumab (MEDI4736) Study Number **ESR-15-11576** Edition Number 5 Date 05/23/16 WFU Date 03/31/17

- History of pneumonitis or interstitial lung disease
- Subjects with uncontrolled seizures
- Uncontrolled intercurrent illness including, but not limited to, ongoing or active infection, symptomatic congestive heart failure, uncontrolled hypertension, unstable angina pectoris, cardiac arrhythmia, active peptic ulcer disease or gastritis, active bleeding diatheses including any subject known to have evidence of acute or chronic hepatitis B, hepatitis C or human immunodeficiency virus (HIV), or psychiatric illness/social situations that would limit compliance with study requirements or compromise the ability of the subject to give written informed consent
- Known history of previous clinical diagnosis of tuberculosis
- Receipt of live attenuated vaccination within 30 days prior to study entry or within 30 days of receiving Durvalumab
- Female subjects who are pregnant, breast-feeding or male or female patients of reproductive potential who are not employing an effective method of birth control
- Patients with body weight < 30 kg
- Any condition that, in the opinion of the investigator, would interfere with evaluation of study treatment or interpretation of patient safety or study results

4.3 Withdrawal of Subjects from Study Treatment and/or Study

An individual subject will not receive any further investigational product if any of the following occur in the subject in question:

- 1. Withdrawal of consent or lost to follow-up
- 2. Adverse event that, in the opinion of the investigator or the sponsor, contraindicates further dosing
- 3. Alterations in treatment, biological samples collection or other study guided investigations that in the opinion of the investigator or the sponsor affects the integrity of the study data collection and analysis
- 4. Subject is determined to have met one or more of the exclusion criteria for study participation at study entry and continuing investigational therapy might constitute a safety risk
- 5. Pregnancy or intent to become pregnant
- 6. Any AE that meets criteria for discontinuation as defined in Section 6.2.1 and Appendix 1.

- 7. Grade \geq 3 infusion reaction
- 8. Subject noncompliance that, in the opinion of the investigator or sponsor, warrants withdrawal; eg, refusal to adhere to scheduled visits
- 9. Initiation of alternative anticancer therapy including another investigational agent
- 10. Confirmation of PD and investigator determination that the subject is no longer benefiting from treatment with Durvalumab
- 11. Surgical treatment is cancelled for any reasons and a tumor biopsy in lieu of surgical specimen cannot be obtained.
- 12. Patients who do not complete at least two administrations of Durvalumab and/or do not submit the biological samples required per protocol.
- 13. Patients who require treatment with steroids for a period longer than 5 days or who receive any steroids within 3 days before surgery.

Subjects who are permanently discontinued from further receipt of investigational product, regardless of the reason (withdrawal of consent, due to an AE, other), will be identified as having permanently discontinued treatment.

Subjects who are discontinued from the study treatment and/or from the study will be replaced.

Subjects who are permanently discontinued from receiving investigational product will be followed for safety per Section 10.3.1 and Appendix 2, including the collection of any protocol-specified blood specimens, unless consent is withdrawn or the subject is lost to follow-up or enrolled in another clinical study. Subjects who decline to return to the site for evaluations will be offered follow-up by phone up to 3 months as an alternative.

Withdrawal of consent

Patients are free to withdraw from the study at any time without prejudice to further treatment.

Patients who withdraw consent for further participation in the study will not receive any further study drug or further study observation. Patient will be asked for permission to use surgical specimen if deemed useful by the investigator.
A patient who withdraws consent will always be asked about the reason(s) for withdrawal and the presence of any AE. The Investigator will follow up AEs outside of the clinical study.

The patient will be replaced in the study.

5. INVESTIGATIONAL PRODUCT

5.1 Durvalumab

The Investigational Products Supply section of AstraZeneca/MedImmune will supply durvalumab to the investigator as a 500-mg vial solution for infusion after dilution.

5.1.1 Formulation/packaging/storage

Durvalumab will be supplied by AstraZeneca as a 500-mg vial solution for infusion after dilution. The solution contains 50 mg/mL durvalumab, 26 mM histidine/histidine-hydrochloride, 275 mM trehalose dihydrate, and 0.02% (weight/volume) polysorbate 80; it has a pH of 6.0. The nominal fill volume is 10 mL. Investigational product vials are stored at 2°C to 8°C (36°F to 46°F) and must not be frozen. Durvalumab must be used within the individually assigned expiry date on the label.

5.1.2 Durvalumab Doses and treatment regimens

Durvalumab every 2 weeks x 2 administrations. A third dose will be allowed in the exceptional cases in which the window time to surgery is longer than 4 weeks. Surgery will follow 3-17 days after the last administration of Durvalumab.

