- a) Clinical toxicity per NCI Common Terminology Criteria for Adverse Events version 4.0 and
- b) Any delays in planned surgery.

Efficacy Assessments:

Response to Durvalumab using CT scan and PET scan

Statistical Methods and Data Anlaysis:

For this pilot study our goal is to get preliminary descriptive data for a series of measures taken using blood, saliva and tumor tissue pre- and post- immunotherapy. With a sample size of 10 patients in each group (i.e. 10 with HPV+ and 10 HPV-) we will be able to estimate a 95% confidence interval for each group with confidence limits +/- 0.72 standard deviations. We can also examine the change in each measure (pre- versus post- therapy) to see whether any confidence intervals show a significant change from baseline (i.e., the measure increased (or decreased) by more than 0.72 standard deviations). This data would provide useful preliminary information concerning the potential mean value and variability for each measure of interest. It may also provide information about which possible measures are most impacted by the intervention within each group (HPV+/HPV-). Furthermore, if we were to compare groups, we would have 80% power to detect a difference in measures equal to 1.3 standard deviations of the measure of interest using a 2-sample t-test with alpha=0.05.

SCHEDULE OF STUDY ASSESSMENTS

Schedule of study assessments: Screening and Treatment Period

			All assessments	to be perfo	med pre-infusion	unless stated	otherwise	
Assessments to be performed at the times stipulated in the table and as clinically required in the management of the subject.	Pre-screening for PD-L1 status ONLY	Screening	Baseline First drug administration	Follow up	Second Drug Administration	Follow up	Before Surgery (3-17 days from last drug adm.)	Surgery
Day	-42 to -1	-28 to -1		Da	y 1 of the week (=	±3 days)		
Week	-6 to -1	-4 to -1	1	2	3	4		
Written informed consent/assignment of subject identification number	X							
Preliminary eligibility fulfilment (investigator's opinion)	Х							
Demography and history of tobacco and alcohol use		Х						
Previous treatments for SCCHN		Х						
HPV by PCR in FFPE	Xa							
Obtain archived or fresh tumour biopsy for PD-L1 assay, if applicable	X							
Formal verification of eligibility criteria		Х						
Medical and surgical history		Х						
Hepatitis A antibody Hepatitis B surface Ag, Hepatitis C antibody and HIV		Х						
Urine hCG or serum βhCG ^b		Х	As clinically indicated					

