3. STUDY DESIGN

3.1 Overview of study design

This is a non-randomized, open label, uncontrolled, single group assignment study, to evaluate the anti-tumor effect of Durvalumab in patients with HNSCC when given as a short treatment course before surgery.

A schematic diagram of the overall study design is shown below.

Patients must be scheduled for surgery and have a window of at least 3 weeks between the time of diagnosis and time of surgery.

In order to be eligible for this clinical study, the patients must have fresh tumor tissue frozen and saved in our Tumor Tissue Bank or need to consent for an additional biopsy procedure to obtain a tumor tissue sample for the clinical protocol that will be saved in our Tumor Tissue Bank for the correlative studies. Patients will undergo an assessment on their tumor tissue sample to determine HPV status.

10 HPV+ and 10 HPV- patients will be initially enrolled and need to complete the study. If any patient does not complete the study treatment and investigations, the patient will be replaced.

First administration of Durvalumab will be given with the first visit after registration with the clinical study. Second administration of Durvalumab will be given 2 weeks later. An interval of 3 to 17 days must be ensured for all patients between the last administration of drug and surgery. A 7-14 days interval will be strongly considered and attempted in each case. In the rare circumstances in which surgery was scheduled or delayed at more than 2 weeks after second administration of Durvalumab, a third administration of drug must be given in order to ensure the proposed interval between the last dose of Durvalumab and surgery.

After surgery the patients may proceed with adjuvant treatment as indicated by the stage of their disease and by the surgical pathology findings. A Radiation Oncologist is included in the study team in order to address and to include in the therapeutic algorithm the impact of the potential cytoreduction by Durvalumab therapy on the final surgical and pathologic staging.

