9.1.2. FDG-PET Scan

PET scan will be obtained before and after treatment whenever approved by Medical Insurance or funded. The initial PET scan should be obtained as close to the treatment start date as possible, with a maximum window period of 28 days. Similar technique and dosing of the 18-Fluoro-deoxyglucose should be targeted. Percentage change in SUV activity between the initial scan (obtained before treatment with Durvalumab) and follow up scan (obtained after treatment with Durvalumab and before surgery) will be reported for each targeted lesions identified on CT scan based on RECIST 1.1.

Little is known about the effect of short course of treatment with Durvalumab on metabolic activity in the tumor. While this can decrease due to inhibition of tumor growth, it is also possible that the metabolic activity measured at primary tumor site and lymph nodes to be increased initially due to increase in number and activity of inflammatory and immune effective cells.

Changes in SUV will be reported to changes in measurements by CT scan or MRI for each lesion.

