11.2.2 Efficacy Analyses

As stated above, there are several primary efficacy measures for this protocol. In addition, this is not a randomized clinical trial, thus there is not one primary efficacy analysis, rather there are a series of primary analyses proposed to be performed examining each of the primary efficacy measures described above.

Analysis of immunogenicity

- Peripheral blood mononuclear cell interferon-γ production in vitro (ELISA) in response to commercially available peptide pools corresponding to HPV, p53, Mage-A3, Her2/neu, and survivin will be compared between patients who are HPV+ and HPV- using 2 sample t-tests. These measures will be compared in several ways. First, baseline, pre-treatment levels will be examined using descriptive statistics (n, mean, standard deviations, range). These measures will be examined overall and by HPV (+/-) groups. For each measure, and time point, 95% confidence intervals will be estimated. Next, two sample t-tests will be performed to compare levels of the measures at baseline. Next, measures taken post-treatment will be examined in a similar manner (descriptive statistics and 2-sample t-tests). Finally, comparisons between HPV+ and HPV- groups will be made by comparing the changes (pre-treatment to posttreatment) between groups using 2-sample t-tests.
- 2) Concentration of certain immune effector and regulatory cells will be assessed in blood (CD4+, CD8+, CD4+FoxP3+ Treg, and CD45RO+CD4+ memory T cells; CD3-CD56+ NK cells, and CD14-HLA-DR-CD15+ MDSC) pre- and post- treatment. Descriptive statistics, confidence intervals will be calculated and 2-sample t-tests will be performed as described above for the interferon- γ analyses.
- 3) Tumor-infiltrating immune-regulator and effector cells will be quantified (0 to 3+) using standing immunofluorescence techniques. Counts and percents will be calculated for these measures overall and by HPV (+/-) groups pre- and post-treatment. Fisher exact tests will be used to compare groups at pre- and post- treatment. Stuart-Maxwell tests (generalizations of the McNemar's Test) will be used to examine changes between groups (HPV +/-) from pre- to post- treatment.

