11.3 Determination of sample size

The goal for this pilot study is to get preliminary descriptive data for a series of measures taken using blood, saliva and tumor tissue pre- and post- immunotherapy. With a sample size of 10 patients in each group (i.e. 10 with HPV+ and 10 HPV-) a 95% confidence interval for each group will have confidence limits $\pm - 0.72$ standard deviations. In addition, the change in each measure (pre- versus post- therapy) can be used to estimate 95% confidence intervals to determine whether there are any significant changes from baseline (i.e., the measure increased (or decreased) by more than 0.72 standard deviations).

Furthermore, to compare groups (HPV+ versus HPV-), there is 80% power to detect a difference in measures equal to 1.3 standard deviations of the measure of interest using a 2-sample t-test with alpha=0.05.

The patients who are discontinued from the study treatment and/or from the study will be replaced.

It is anticipated that an accrual rate of 12 patients per year is reasonable and thus the goal of 20 evaluable patients should be achieved within approximately 18 months. Additional 6 mo might be needed for accruing replacement patients for the patients unable to complete study treatment or required investigations.

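### HPV contrasts of post-treatment values and changes take no account of days since last dose (3-17) or of two versus three doses, so unequal timing could mimic or mask an HPV effect

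*Combined protocol and SAP*

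**What the plan says.** - **Timing.** Section 5.1.2: "Surgery will follow 3-17 days after the last administration of Durvalumab". In the Schedule of Study Assessments the pre-surgery visit, with post-treatment blood, saliva, CT or MRI and PET, carries the same 3-17 day window. The post-treatment tumor sample is the surgical specimen (11.1, primary endpoints).
- **Target.** Section 3.1: "A 7-14 days interval will be strongly considered and attempted in each case". This is an aim, not a requirement.
- **Dose count.** Two doses are planned and a third is possible. The efficacy set in 11.1.2 takes everyone with at least two doses, so both kinds of patient are pooled.
- **Analysis.** For interferon-gamma, section 11.2.2 says "comparisons between HPV+ and HPV- groups will be made by comparing the changes (pre-treatment to posttreatment) between groups using 2-sample t-tests". Blood cell counts, miR levels, CT and PET follow the same pattern. The 0-3+ tissue scores get Fisher exact and Stuart-Maxwell tests. Nothing in 11.2 adjusts for, restricts by or tabulates the interval or the number of doses.
- **Expected time course.** Section 9.1.2 allows that metabolic activity may fall, but also that it may turn out "to be increased initially due to increase in number and activity of inflammatory and immune effective cells".

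**The concern.** The protocol treats the interval as important: it sets a preferred range and, in section 3.1, links the third dose to keeping the interval. The analysis then treats all post-treatment measurements as taken at the same point.

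The interval follows the surgical calendar, and HPV status is not randomised. Section 4.1 ties HPV status to site (oral cavity more than 90% HPV negative, oropharynx about 60-80% positive) and admits both robotic and standard surgery. Nothing in the design balances timing between the groups.

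The differential effect by HPV status is part of the primary objective and is meant to inform later trials (1.4, 2.1). A time effect shared by both groups could be carried forward as an HPV effect, or could cancel a real one. Baseline contrasts are not affected.

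**Working it through.** **Inputs from the documents.** "With a sample size of 10 patients in each group" (11.3); interval 3-17 days, a 14-day spread (5.1.2); doses two weeks apart (3.1). The documents give no rate of change over the window and no interval by HPV group, so both are assumed below.

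**1. The plan's own figures.**
- The synopsis states "we will be able to estimate a 95% confidence interval for each group with confidence limits +/- 0.72 standard deviations". Check: t(0.975, 9 df)/√10 = 0.715 SD, which rounds to 0.72.
- Section 11.3 states "there is 80% power to detect a difference in measures equal to 1.3 standard deviations of the measure of interest using a 2-sample t-test" at alpha 0.05. Noncentral t, 18 df, noncentrality 1.3/√(2/10), two-sided: 78.5%. Exactly 80% needs 1.32 SD. Both figures reproduce within rounding.

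**2. Calendar spread.** With doses on days 0 and 14, surgery falls 14+3 = 17 to 14+17 = 31 days after the first dose. With a third dose on day 28 it falls at 31 to 45 days. The overall range is 17-45 days.

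**3. False difference from timing alone.** Let D be the drift in SD over 14 days and g the gap in mean interval between groups. Bias = D × g/14. The false-positive rate is the two-sided t-test rejection rate with noncentrality bias/√(2/10), 18 df. For D = 1 and no HPV effect:

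| Gap g (days) | Bias (SD) | False positives (nominal 5%) |
|---|---|---|
| 2 | 2/14 = 0.14 | 6% |
| 3.5 | 3.5/14 = 0.25 | 8% |
| 5 | 5/14 = 0.36 | 12% |
| 7 | 7/14 = 0.50 | 18.5% |

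Simulation with intervals uniform on (3, 17−g) and (3+g, 17) gives about 12% at 5 days and 18% at 7. At D = 0.5, a 7-day gap gives 0.25 SD and 8%. With no drift or no gap the bias is zero. If all patients fall within 7-14 days, complete separation of the groups is a 3.5-day gap, so the first two rows are the relevant ones.

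**4. Masking.** If a true 1.3 SD difference runs against a 1 SD drift with a 5-day gap, the expected difference is 1.3 − 0.36 = 0.94 SD and power falls from about 78% to about 50%.

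**5. Third dose.** Suppose it adds 0.5-1 SD and 1-3 of 10 patients in one group only receive it. Bias = effect × k/10 = 0.05-0.30 SD, with 5-10% false positives.

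**6. What adjustment buys and costs.** With days since last dose as a linear covariate and a linear drift, simulated false positives return to about 5%. In SD² units, the variance of the contrast rises from 2/10 to about 2/10 + g²/Sxx, where Sxx is the within-group sum of squares of the interval, about 18 × (14−g)²/12. At g = 5, Sxx = 121.5 and the variance is 0.2 + 25/121.5 = 0.41, about double. Simulated power at 1.3 SD:

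| Gap g (days) | Adjusted power |
|---|---|
| 0 | 76% |
| 3 | 68% |
| 5 | 49% |
| 7 | 26% |

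**7. Non-linear course.** Take a 1 SD rise from day 3 to day 8, then a fall to zero at day 17, with g = 7. The bias is 0.22 SD unadjusted and about 0.32 SD after linear adjustment. The linear term does not remove it and here enlarges it.

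**The case against.** This is a pilot whose stated goal is descriptive data, with no single primary efficacy analysis (11.1, 11.3). The 7-14 day target, if met, halves the spread and leaves little inflation at a 1 SD drift. The third dose is called rare or exceptional. The schedule also takes immune and miRNA blood at week 4, a fixed time for two-dose patients. With 10 per group, a covariate model can cost far more power than it saves.

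Much of this stands. It rules out replacing the t-tests with an adjusted model as the main analysis. It does not justify leaving timing unreported. The target is not binding. Section 9.2 takes the pre-surgery blood as the post-treatment sample, flow cytometry is scheduled only at baseline and before surgery, and tumor has no fixed-time alternative.

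Two stronger readings are tempting. A reader might infer from the link between HPV status and tumor site, or from the two surgical techniques, that the groups will be operated on at different intervals; the documents say nothing on this. A reader might also take section 9.1.2 as evidence of a drift between days 3 and 17. It offers an early rise only as a possibility, and says that little is known.

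**Conclusion.** The gap is real but conditional. Post-treatment and change contrasts between HPV groups ignore days since last dose and number of doses, and nothing in the plan would show whether these differ. The size depends on two assumed quantities. At a 1 SD linear drift, false positives are about 12-18% for gaps of 5-7 days and about 6-8% if the 7-14 day target holds throughout. Interval probably matters more than dose count, since third doses should be few.

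It would be wrong to conclude that a covariate removes the problem for about two points of power. The 76% figure needs balanced timing, the very case in which adjustment is not needed for bias, and the return to 5% relies on a linear drift. Adjustment reduces and exposes the bias. The low power at large gaps reflects how far HPV status and timing would then be confounded.

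**What to change.** Keep the planned t-tests and add to section 11.2.2:

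1. A table, by HPV group, of days from last dose to each post-treatment sample or scan, and of number of doses.
2. Two pre-specified sensitivity analyses: (a) for the continuous measures, a linear model of change on HPV group and days since last dose; (b) all HPV contrasts, including the 0-3+ tissue scores, in two-dose patients only.
3. A statement that a difference will not be attributed to HPV status if timing differs between the groups or the sensitivity results disagree with the main ones.

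The passages on a third dose must also be reconciled, because the dose count for a given surgery date depends on which is followed. The synopsis and 5.1.2 allow it when the window to surgery exceeds 4 weeks. Section 3.1 requires it when surgery is more than 2 weeks after the second dose. Section 6.2 has it considered beyond 17 days.

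The cost is SAP wording and a little more analysis of dose, sample, scan and surgery dates. The adjusted contrast will be imprecise if timing is unbalanced (step 6 of the working) and should be reported with that caveat.
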